11.3 Suspected Unexpected Serious Adverse Reaction (SUSAR)

A SUSAR is a serious adverse event which is both suspected as being related to the drug (i.e. has a reasonable suspected causal relationship and is unexpected) and where the nature and severity is not consistent with known information (e.g. the Investigator's Brochure for an unapproved investigational product or Product Information for an approved product) about the drug in question.

11.3.1 Reporting of SUSARs

The Project Team in collaboration with the Medical Officer will review and identify all serious events which fit the criteria of a SUSAR and require expedited reporting to relevant parties. The event will be designated as unexpected if it is not reported in the Investigator Brochure or Product Information or if the event is of greater frequency, specificity or severity.

The Sponsor must expedite the reporting of all suspected unexpected and certainly, probably, possibly, or of undetermined relationship to the study drug to all concerned investigators/institutions, IRB/IEC/s, and regulatory authorities within 7 days if it is life-threatening or fatal or within 15 days if not. Reports must comply with the applicable regulatory requirements and ICH Guideline for Clinical Safety Data Management: Definitions and Standards for Expedited Reporting.

Researchers must inform the IRB/IEC and regulatory authorities of all serious or unexpected AEs that occur during the study which may affect the conduct of the study or the safety of the participants and/or their willingness to continue participation in the study.

11.4 Serious Non-AIDS events (SNAEs) and AIDS events

SNAEs are defined as fatal and non-fatal diagnoses in the following categories (see Appendix 4 for details):

- Acute myocardial infarction
- Coronary artery disease requiring drug treatment
- Stroke
- Coronary revascularisation
- Congestive heart failure
- Deep vein thrombosis
- Peripheral arterial disease
- Pulmonary embolism
- End stage renal disease
- Decompensated liver disease
- Non-AIDS defining malignancy (except non-invasive basal cell carcinoma or squamous cell carcinoma)
- Diabetes mellitus

- AIDS events (CDC Category C 1993 Definition – see Appendix 3):
 - Candidiasis of bronchi, trachea, or lungs
 - Candidiasis, oesophageal
 - Cervical cancer, invasive
 - Coccidioidomycosis, disseminated or extrapulmonary
 - Cryptococcosis, extrapulmonary
 - Cryptosporidiosis, chronic intestinal (> 1 month's duration)
 - CMV disease (other than liver, spleen, or nodes)
 - CMV retinitis (with loss of vision)
 - Encephalopathy, HIV-related (including AIDS Dementia Complex)
 - Herpes simplex, chronic ulcers (> 1 month's duration); or bronchitis, pneumonitis, or esophagitis
 - Histoplasmosis, disseminated or extrapulmonary
 - Isosporiasis, chronic intestinal (> 1 month's duration)
 - Kaposi's sarcoma (mucocutaneous or visceral)
 - Lymphoma, Burkitt's (or equivalent term)
 - Lymphoma, primary, of brain
 - Mycobacterium avium complex or M. kansasii, disseminated or extrapulmonary
 - M. tuberculosis, any site (pulmonary or extrapulmonary)
 - Mycobacterium, other species or unidentified species, disseminated or extrapulmonary
 - Pneumocystis carinii (jiroveci) pneumonia
 - Pneumonia, recurrent bacterial (2 documented episodes within 1 year of each other following randomisation)
 - Progressive multifocal leukoencephalopathy
 - Salmonella septicaemia, recurrent (2 documented episodes within 1 year of each other following randomisation)
 - Toxoplasmosis of brain
 - Wasting syndrome due to HIV
 - Aspergillosis, invasive
 - Bartonellosis
 - Chagas disease (American trypanosomiasis) of the CNS
 - Herpes zoster, multi-dermatomal (≥ 10 lesions in a non-contiguous site)
 - Leishmaniasis, visceral (kala-azar)
 - Lymphoma, Hodgkin's
 - Lymphoma, non-Hodgkin's, all cell types
 - Microsporidiosis (> 1 month's duration)
 - Nocardiosis
 - Penicillium marneffii, disseminated
 - Pneumocystis carinii (jiroveci), extrapulmonary
 - Rhodococcus equi disease

11.4.1 Reporting of SNAEs and AIDS defining illnesses

All SNAEs and AIDS defining illnesses must be reported to the Kirby Institute as per SAE reporting outlined in section 11.2.1. Details of how to report these will be outlined in the MOOP.

11.5 Reporting of pregnancy

There are no clinical studies in the use of vorapaxar in pregnant women. Studies in rats and rabbits showed no embryo/foetal toxicities, malformations or maternal toxicities when exposed to high doses of vorapaxar during gestation.

As there is a paucity of data on vorapaxar in pregnancy, sexually active women of childbearing potential must use an effective method of birth control during the course of the study, in a manner such that risk of pregnancy is minimised. Women will undergo a urine dipstick or serum pregnancy test at each visit (except week 1) and if found to be pregnant during follow-up should be managed in keeping with prevailing national or international guidelines. At a minimum, women must immediately cease study medication.

All pregnancies on study are subject to expedited reporting and therefore the serious event form will need to be completed and submitted to The Kirby Institute within 24 hours (one working day) of becoming aware of the pregnancy. In addition, it is requested that information from any pregnancy on study be recorded on the appropriate page of the eCRF. It is the responsibility of investigators or their designees to report any pregnancy in a subject/patient (spontaneously reported to them) which occurs during the study (from screening until the week 18 visit). All subjects/participants who become pregnant must be followed to the completion/termination of the pregnancy. If the pregnancy continues to term, the outcome (health of infant) must also be reported to The Kirby Institute.

It is requested that information from any pregnancy on study be recorded on the appropriate page of the electronic CRF. Anonymised data from these forms will then be transmitted by the Kirby Institute to the Antiretroviral Pregnancy Register, an international register making a systematic attempt to collect data on pregnancy, ART and outcomes. Submission of data to the registry is encouraged, but not mandated by the study and a participant may choose not to have their data submitted. The scientific conduct and analysis of the Registry are overseen by an Advisory Committee consisting of members from the Centers for Disease Control and Prevention (CDC), Food and Drug Administration (FDA), the National Institutes of Health (NIH) as well as the private sector (<http://www.apregistry.com/>).

11.6 Definition and reporting of an overdose

In previous studies, vorapaxar has been given in single doses up to 120mg and daily doses of 5mg for up to 4 weeks without identification of a specific risk or dose related adverse events. However, for the purposes of this study, an overdose of vorapaxar is defined as 3 doses (7.5mg) or more within 24 hours. Any overdose, whether or not associated with an adverse reaction, must be reported within 24 hours on the paper SAE form to the Kirby Institute and the participant monitored closely for signs and symptoms of adverse reactions and appropriate clinical care given

There is no known treatment to reverse the antiplatelet effect of vorapaxar. Dialysis or platelet infusion is not expected to be beneficial if bleeding occurs after an overdose. Monkey data suggest that platelet transfusions of sufficient quantity (a full pheresis pack or two) have the potential to transiently (a few hours) reverse the antiplatelet activity of vorapaxar. There is no standard test available to assess the risk of bleeding in case of an overdose.

11.7 Unblinding

The necessity to unblind the participant's randomisation prior to reporting Serious Events will be considered on a case-by-case basis by the Medical Officer, site Principal Investigator and the expertise of members of the

Protocol Steering Committee. Where unblinding is authorised by the Project Leader, it will be undertaken by a statistician. If the Project Leader does not authorise unblinding, the Serious Event reporting form should indicate that the study is blinded and that the participant may be on placebo or vorapaxar.

In case of emergency, the Principal Investigator should contact the Kirby Institute to request unblinding where it is essential to know what treatment the participant is on to decide on the medical interventions required. Access to the code break procedures must be available on a 24-hour basis.

At the conclusion of the study, after the clinical database is locked, treatment allocation information will be given to participating centres.

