10.3.2.4 BARC Type 4 Bleeding

Any participant who is planning to undergo any planned surgical procedure 6 months after the planned randomisation should not be enrolled into the study. If there is a need for a participant to undergo an emergency CABG or any other surgical procedure during the course of the study, the study drug should be immediately and permanently discontinued. If deemed necessary, unblinding procedures could be initiated but attention to how best do this will be given to avoid site staff becoming aware of the treatment allocation.

It is important that the treating physician is informed that vorapaxar results in residual platelet aggregation activity 4 weeks after stopping and appropriate clinical decisions are made. There is no known antidote for vorapaxar. It is the investigator’s responsibility to inform the treating physician of this.

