5.2 Adverse Events

Bleeding adverse events

Total number of participants with Type 1, 2, 3, 4 or 5 bleeding episodes using BARC criteria. Bleeding episodes will be summarised by type and randomised treatment.

Serious Adverse Events

Total number of participants with any Serious Adverse Event (SAE) and the cumulative incidence of SAEs. SAEs will be summarised by randomised treatment and relationship to study drug.

Adverse events

Total number of participants with any Adverse event (AE) and the cumulative incidence of AEs. All AEs, and grade 3 or 4 AEs, will be summarised by MedDRA group term, relationship to study drug and randomised treatment.

Laboratory adverse events

Total number of participants with laboratory or biochemical adverse events, according to DAIDS criteria, in particular renal function measured by the CKD-EPI estimate of creatinine clearance. Laboratory AEs will be summarised by grade and randomised treatment.

Statistical analysis of adverse event data

The proportion of patients with adverse events will be compared between randomised treatments using chi-square tests, Fisher's exact test or similar as appropriate to the data. Differences in proportions of patients with events by randomised treatments will be summarised as 95% confidence intervals.

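### Section 11.7 allows non-emergency unblinding before a serious event is reported, without requiring causality to be recorded first or saying who learns the allocation, so tabulations by relationship to study drug are open to assessment bias

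*Protocol*

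**What the plan says.** Protocol 11.7 has two routes to unblinding.

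- **Before a serious event is reported.** The need to unblind the participant's "randomisation prior to reporting Serious Events will be considered on a case-by-case basis by the Medical Officer, site Principal Investigator" and members of the steering committee. The gatekeeper and operator are named: "Where unblinding is authorised by the Project Leader, it will be undertaken by a statistician". If authorisation is refused, "the Serious Event reporting form should indicate that the study is blinded and that the participant may be on placebo or vorapaxar". No criterion for granting it is given.
- **Emergency.** The site principal investigator contacts the coordinating centre to "request unblinding where it is essential to know what treatment the participant is on to decide on the medical interventions required".

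Two other sections deal with breaking the blind for an individual. In 10.3.2.4 (surgery and BARC type 4 bleeding), "attention to how best do this will be given to avoid site staff becoming aware of the treatment allocation". In 10.3.2.5, a fatal bleed leads to the code being broken for that participant.

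Relatedness is used in three places. Protocol 6.2.2 summarises adverse events by relation to study drug. Protocol 11.3.1 has the project team and the Medical Officer identify SUSARs, for which suspected causality is a defining element (11.3). SAP 5.2 states that "SAEs will be summarised by randomised treatment and relationship to study drug".

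**The concern.** Whether an event is related to study drug is a matter of judgement, and it is protected from knowledge of treatment only if it is made blind. An event known to have occurred on placebo cannot credibly be attributed to vorapaxar. A bleed known to have occurred on vorapaxar invites attribution, because bleeding is the drug's recognised risk (protocol 3.3 and 10.3.2) and the stated focus of the safety analysis (6.2.2).

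Section 11.7 places the possible code break before the report. The people who consider it include the site principal investigator, whose side of the trial judges causality (10.2.2, 10.2.3, 11.1.1), and the Medical Officer, who also takes part in SUSAR review. If either learns the allocation before the judgement is fixed, the split of SAEs by relationship can reflect who was unblinded as well as what the drug did. With about 30 participants per arm, one participant is 1/30 = 3.3 percentage points, so a sparse table is easily tilted.

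**Working it through.** The plan states no figure on this point, so there is none to reproduce. The check is a reading of the text, followed by an illustration of possible size.

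**Text**

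1. *Is unblinding before reporting permitted outside an emergency?* Yes. The first paragraph of 11.7 deals with it case by case. The need to decide medical interventions appears only in the second paragraph.
2. *Can the allocation be known when the form is completed?* By implication, yes. The instruction to mark the form as blinded applies only when authorisation is refused.
3. *Must relatedness be fixed first?* No section of the protocol or SAP says so. The same holds for the fatal-bleed code break in 10.3.2.5.
4. *Who receives the allocation?* 11.7 names who authorises and who carries out the unblinding, but not who is told. The aim of keeping site staff unaware is written only in 10.3.2.4.
5. *What depends on relatedness?* Protocol 6.2.2, protocol 11.3.1 and the relationship split in SAP 5.2. The SAE endpoint (protocol 5.5, SAP 5.2) counts participants with any SAE, and 11.2.1 requires SAEs to be reported whatever the suspected causality. The primary endpoint uses d-dimer measured centrally on stored plasma (13.7).

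**Size (illustration)**

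From the documents: 60 participants randomised 1:1 (protocol 6.1 and 8.0), so 30 per arm.

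Assumed, because the documents give no values:

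- the same true SAE risk *s* in both arms, 3% to 20%;
- a share *u* of SAEs unblinded before reporting, 10% to 100%;
- 30% called related when judged blind;
- when judged unblinded, 60% called related on vorapaxar and 0% on placebo.

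Expected participants with a related SAE:

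- vorapaxar: 30 × *s* × [(1 − *u*) × 0.30 + *u* × 0.60]
- placebo: 30 × *s* × (1 − *u*) × 0.30
- excess: 30 × *s* × *u* × 0.60 (the blinded share cancels)

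| *s* | *u* | Vorapaxar | Placebo | Spurious excess |
|---|---|---|---|---|
| 3% | 10% | 0.297 | 0.243 | 0.054 |
| 10% | 25% | 1.125 | 0.675 | 0.45 |
| 10% | 50% | 1.35 | 0.45 | 0.90 |
| 20% | 100% | 3.60 | 0 | 3.60 |

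The difference in any-SAE counts stays at 0 throughout, because relatedness does not enter it.

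For scale, Fisher's exact test (two-sided) at 30 v 30 gives p = 0.112 for 4 v 0, p = 0.052 for 5 v 0 and p = 0.024 for 6 v 0. An artefact would have to reach 6 v 0 to cross 0.05, above the largest expected value in the table.

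**The case against.** The strongest reply is that this route is narrow. It is considered case by case, needs the Project Leader's authorisation and is carried out by a statistician. The protocol otherwise protects the blind: SAE line listings omit treatment group (11.2.1), and centres receive allocations only after database lock (11.7). The text can also be read as meant for expedited reporting. The Manual of Operations, which is not available here, may settle the order of steps and the recipient. All of this stands and limits the likely effect. It does not supply the missing order or the missing recipient, and 11.7 does not refer to the Manual for either.

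A reader might go further in four ways that the documents do not support.

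- *A related-SAE comparison is biased.* No such endpoint or test is named. SAP 5.2 tabulates by relationship. Its general test concerns the proportion of patients with adverse events and could only be stretched to cover related ones. Nor does the text say that the person judging relatedness receives the code. The supportable claim is that bias is possible.
- *Steering committee members learn allocations.* 11.7 involves them in considering whether unblinding is necessary. It does not say they are told the result.
- *11.7 contradicts 10.3.2.4.* 11.7 never says site staff are told. It is silent on a protection that 10.3.2.4 states, which is a gap and not a conflict.
- *BARC typing is compromised as well.* Types 3 to 5 rest largely on objective criteria such as haemoglobin drop, transfusion, surgery, imaging or death (Appendix 2), and 10.3.2 calls for a haemoglobin sample when a clinically significant bleed is suspected. Type 1 bleeds involve no hospitalisation or treatment, so they would rarely enter serious-event reporting.

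**Conclusion.** The point holds as a weakness in a stated procedure. Section 11.7 lets the code be broken before a serious event is reported, outside an emergency, without first fixing the causality judgement and without saying who learns the allocation. The SAE table by relationship, the adverse event summary by relation to study drug and SUSAR identification are open to assessment bias as a result. The any-SAE endpoint and the d-dimer primary endpoint are not.

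The size cannot be derived from the documents. The range of about 0.05 to 3.6 participants rests entirely on the assumed SAE risk, unblinding share and relatedness shares. Its upper end needs every SAE to be unblinded before reporting, which sits badly with a case-by-case rule, so values towards the lower end are more plausible. This is a cheap improvement and does not threaten the trial's main conclusions.

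**What to change.** In protocol 11.7:

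- require the investigator's relatedness assessment to be recorded and dated on the Serious Event form and in the eCRF before any non-emergency code break. The form must be covered because 11.2.1 has SAEs reported on it by telephone, email or fax;
- state that the allocation goes only to those who need it to file the report, with site staff kept unaware as 10.3.2.4 intends;
- leave emergency access unchanged, but flag any assessment made after unblinding, including after the fatal-bleed code break in 10.3.2.5.

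In SAP 5.2, use the pre-unblinding assessment for the relationship table and mark each SAE whose relatedness was assessed after unblinding.

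The cost is one dated field and a few sentences. Reporting need not be delayed, since suspected causality has to be judged anyway before an event can be classed as a SUSAR. The SAP change can still be applied late in the trial if the dates of assessment and of any code break are on record.

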12.0 Packaging, labelling, storage and accountability of clinical trial supplies

12.1 Drug packaging, labelling and distribution

Study drug will be sent to nominated pharmacies at study sites in accordance with the random allocation, following receipt of orders from recognised study staff. A designated person at the pharmacy must receive investigational drug supplies. The designated person must check that the supplies are in good condition and are complete as per the shipping records. Investigational drugs must be stored in a secure location with limited access and according to the drug requirements and local regulations.

Further detailed information on the packaging, labelling and distribution of the study drug will be outlined in the MOOP and dealt with in detail during the site initiation process. Distribution and receipt of the study drugs will be at no cost to study sites.

12.2 Handling and dispensing of study drugs

Study drugs must only be dispensed according to the protocol and MOOP. It is the responsibility of the Investigator to ensure that study drug is only dispensed to study participants and only dispensed by suitably trained, authorised personnel according to local regulations at recognised hospital and clinic pharmacies.

Study drugs should only be dispensed on receipt of a prescription written by the Principal Investigator or designee at the site. This prescription must contain the unique participant identification number.

The participant must be instructed to take the study drug tablets whole and to store all medication safely out of sight and reach of children.

Once the participant has been randomised, a one month blinded supply of vorapaxar or placebo will be dispensed to the participant from clinical supplies stored at the study site. At each subsequent visit, participants will be required to return empty, partially used and unused study drug containers that will be retained at the site for later destruction at the approval of the Sponsor. Records must be kept of unreturned study drug and/or containers. No drugs will be returned to the Sponsor.

At each dispensing, participants should be counselled on adherence issues. All participants should be counselled regularly on the need for maintaining strict adherence with the allocated study regimens. The objective should be 100% adherence at all times during follow-up. The site Principal Investigator is responsible for assessing adherence with all aspects of the study including use of study drugs and attendance at protocol-mandated clinical visits and assessments.

The Investigator must be satisfied that the participant has returned or accounted for all unused study drug before additional medication is dispensed. If the number of encapsulated tablets recorded as used is substantially different from the number prescribed, the participant must be counselled on how study drugs should be taken. If such deviations persist, the Investigator may consider discontinuing the regimen for non-adherence. If this occurs, the participant must remain in follow-up and undergo the protocol-specified assessments and evaluations.

12.3 Study drug accountability records at investigational site(s)

It is the responsibility of the Principal Investigator to ensure that a current record of study drug disposition is maintained at each study site where they are inventoried and disposed. Records and/or logs must comply with applicable regulations and guidelines, and should include:

- Amount received from the sponsor and placed in storage area (temperature logs to be kept to document appropriate storage conditions)
- Label ID number or batch number
- Amount dispensed to and returned by each participant, including unique participant identifiers
- Non-study disposition (e.g. lost, wasted, broken)
- Amount destroyed at study site (with Sponsor authorisation), as applicable.
- Dates and initials of person responsible for each investigational product inventory entry/movement

The Kirby Institute will provide forms to facilitate inventory control. Please refer to the MOOP for further details.

12.4 Destruction of study drug

Study drugs will not be returned to the Kirby Institute for destruction. Instead, it will be destroyed at site after reconciliation has been conducted by the study monitor. For further details of destruction of study medications, please refer to the MOOP.

